### **7.3 Participant departure from vaccination schedule or withdrawal**

This section concerns an individual participant's departure from the study product administration schedule. Pause rules for the trial are described in Section [11.3](#).

#### **7.3.1 Delaying vaccinations for a participant**

Under certain circumstances, a participant's scheduled vaccination will be delayed. The factors to be considered in such a decision include but are not limited to the following:

- Within 45 days prior to any study injection
  - Receipt of blood products or immunoglobulin
- Within 30 days prior to any study injection
  - Receipt of other vaccines (eg, influenza, tetanus, pneumococcal, Hepatitis A or B, MMR; OPV; varicella; yellow fever)
  - Receipt of allergy treatment with antigen injections
- Prevacination abnormal vital signs or clinical symptoms that may mask assessment of vaccine reaction.

Vaccinations should not be administered outside the visit window period specified in the HVTN 121 *Study Specific Procedures*.

In order to avoid vaccination delays and missed vaccinations, participants who plan to receive licensed vaccines or allergy treatments should be counseled to schedule receipt of these substances, when possible, outside the intervals indicated above. The effects of these substances on safety and immunogenicity assessments and their interactions with study vaccines are unknown; for example, reactions to these substances could be misattributed to study product. Therefore, if circumstances allow, these substances should also be avoided in the 30 days after a study vaccination.

#### **7.3.2 Participant departure from vaccination schedule**

Every effort should be made to follow the vaccination schedule per the protocol. If a participant misses a vaccination and the visit window period for the vaccination has passed, that vaccination cannot be given. The participant should be asked to continue study visits. The participant should resume the vaccination

schedule with the next vaccination unless there are circumstances that require further delay or permanent discontinuation of vaccination (see Sections 7.3.1 and 7.3.3).

However, missed vaccinations may be indicative of medical or social circumstances that indicate the participant should be excluded from future vaccination, and the study team should take this into account when assessing missed vaccinations.

### 7.3.3 Discontinuing vaccination for a participant

Under certain circumstances, an individual participant's vaccinations will be permanently discontinued. Specific events that will result in stopping a participant's vaccination schedule include:

- Co-enrollment in a study with an investigational research agent (rare exceptions allowing for the continuation of vaccinations may be granted with the unanimous consent of the HVTN 121 PSRT)
- Clinically significant condition (ie, a condition that affects the immune system or for which continued vaccinations and/or blood draws may pose additional risk), including but not limited to the following:
  - Pregnancy (regardless of outcome)
  - HIV infection
  - Any grade 4 local or systemic reactogenicity symptom, lab abnormality, or AE that is subsequently considered to be related to vaccination
  - Any grade 3 lab abnormality that is subsequently considered to be related to vaccination
  - Other grade 3 clinical AE that is subsequently considered to be related to vaccination with the exception of fever, vomiting, and subjective local and systemic symptoms. For grade 3 injection site erythema and/or induration, upon review, the HVTN 121 PSRT may allow continuation of vaccination
  - SAE that is subsequently considered to be related to vaccination
  - Clinically significant type 1 hypersensitivity reaction associated with study vaccination. Consultation with the HVTN 121 PSRT is required prior to subsequent vaccinations following any type 1 hypersensitivity reaction associated with study vaccination
  - Related "Severe" SLE flare, as defined by application of the SELENA-SLEDAI instrument ([Appendix G](#))
  - SLE flare is defined clinically by a rheumatologist as severe enough to warrant discontinuation of vaccination
  - New use of mycophenolate mofetil

- Investigator determination in consultation with Protocol Team leadership (e.g., for repeated nonadherence to study staff instructions)

Participants discontinuing study product for reasons other than HIV infection should be counseled on the importance of continuing with the study and strongly encouraged to participate in follow-up visits and protocol-related procedures per the protocol for the remainder of the trial, unless medically contraindicated (see HVTN 121 SSP).

Participants diagnosed with HIV infection during the study should be encouraged to participate in follow-up visits as indicated in Section [9.12](#).

#### **7.3.4 Participant termination from the study**

Under certain circumstances, an individual participant may be terminated from participation in this study. Specific events that will result in early termination include:

- Participant refuses further participation,
- Participant relocates and remote follow-up is not possible,
- HVTN CRS determines that the participant is lost to follow-up, or
- Investigator decides, in consultation with Protocol Team leadership, to terminate participation (eg, if participant exhibits inappropriate behavior toward clinic staff).
- Any condition where termination from the study is required by applicable regulations.

## 8 Study product preparation and administration

CRS pharmacists should consult the Pharmacy Guidelines and Instructions for DAIDS Clinical Trials Networks for standard pharmacy operations. The protocol schema is shown in [Table 3-1](#). See the Investigator's Brochures (IB) for further information about study products.

### 8.1 Vaccine regimen

The schedule of vaccination is shown in [Section 3](#) and additional information is given below.

AIDSVAX® B/E (600 mcg/mL) to be administered as a 1 mL IM injection into the deltoid of the non-dominant arm (unless medically contraindicated) at months 0, 1, and 6.

### 8.2 Study product formulation

Please refer to the IB for additional information about study product.

**AIDSVAX® B/E (labeled as AIDSVAX® B/E active (MN/A244 rgp 120/HIV-1))** is supplied as a 600mcg/mL sterile suspension in single-use glass vials with a volume to deliver 1 mL consisting of 300 mcg of subtype B (MN) HIV gp120 glycoprotein and 300 mcg of subtype E (A244) HIV gp120 glycoprotein adsorbed onto a total of 600 mcg aluminum as aluminum hydroxide gel suspension as adjuvant. Product is a white to slightly grey suspension with possible product-related particles. Some gel may be visibly adhering to the sides and neck of the vial and should be resuspended using the recommended protocol. The product must be stored upright and kept refrigerated (2° to 8°C). Do not freeze. Do not shake.

### 8.3 Preparation of study product

#### 8.3.1 AIDSVAX® B/E

One vial of AIDSVAX® B/E will be needed to prepare the dose.

Prior to dispensing, the pharmacist will remove the study product from the refrigerator to allow the vial to equilibrate to room temperature for at least 20 minutes. The pharmacist must then:

1. Gently roll the vial horizontally between the palms or on a hard surface for approximately 10 seconds to wet the interior wall of the vial and to suspend the material.

2. Grasp the vial by the sides. Firmly and forcefully tap the bottom of the vial on a solid surface such that the vial hits squarely on a solid surface, in a rapid series of three (3) taps. Tap with enough force to dislodge any material that may be on the sides of the vial while using care not to chip or break the vial.
3. Repeat the gentle rolling and forceful tapping two more times, resulting in one (1) cycle of 9 taps.
4. Visually inspect the neck of the vial for presence or absence of product-related material (grayish film) as well as the sides of the vial. Vaccine that is stored at 2°C to 8°C can form an appearance of a cloudy ring or ‘halo’ on the vial neck and/or have product related material adhering on the sidewalls. If either scenario is observed, the pharmacist should continue to follow the steps as directed below to dislodge and uniformly resuspend such product-related material.
5. If residual product-related material still persists at the neck/sides of the vial at the end of the first cycle, repeat steps 1 to 4, for up to two (2) more cycles.
6. If the product-related material is still visible at the end of the third repeated cycle DO NOT use the vial.

After completing these steps, the pharmacist, using aseptic technique, will gently roll the mixture in the vial one more time and then withdraw 1 mL into a 3mL syringe using a 21 or 23 gauge needle.

The syringe should be labeled as “AIDSVAX® B/E 600 mcg.” The syringe must also be labeled “for administration into the deltoid of the non-dominant arm.” The study product should be administered within 2 hours of being drawn into the syringe.

Any unused portion of entered vials or expired prefilled syringes should be autoclaved immediately prior to disposal and disposed of in accordance with institutional or pharmacy policy. If they will be incinerated, they do not need to be autoclaved.

#### **8.4 Administration**

When preparing a dose in a syringe and administering the dose, consideration should be given to the volume of solution in the needle before and after the dose is administered. Particularly, if the needle used to withdraw the product is replaced prior to vaccine administration, consideration should be given to conserving the full dose of product. The pharmacy and clinic staff members are encouraged to work together to administer the dose specified in the protocol.

For all AIDSVAX B/E injections, the person administering the injection should gently roll the syringe prior to administration of the study product. For these injections, a 21 or 23 gauge needle must be used for administration.

Vaccines will be injected intramuscularly (IM) into the deltoid muscle of the non-dominant arm.

AIDSVAX® B/E will be administered on months 0, 1, and 6.

## **8.5 Acquisition of study products**

AIDSVAX® B/E will be provided by GSID (San Francisco, California, USA).

Once an HVTN CRS is protocol registered, the pharmacist can obtain study products from the NIAID Clinical Research Products Management Center (CRPMC) by following the ordering procedures outlined in Pharmacy Guidelines and Instructions for DAIDS Clinical Trials Networks.

## **8.6 Pharmacy records**

The HVTN CRS pharmacist is required to maintain complete records of all study products. The pharmacist of record is responsible for maintaining randomization codes and randomization confirmation notices for each participant in a secure manner.

## **8.7 Final disposition of study products**

For US clinical research sites, all unused study products must be returned to the CRPMC after the study is completed or terminated unless otherwise instructed by the study sponsor. The procedures are included in the Pharmacy Guidelines and Instructions for DAIDS Clinical Trials Networks.

## 9 Clinical procedures

The schedule of clinical procedures is shown in [Appendix F](#).

### 9.1 Informed consent

Informed consent is the process of working with participants so that they fully understand what will and may happen to them while participating in a research study. The HVTN informed consent form (ICF) documents that a participant (1) has been informed about the potential risks, benefits, and alternatives to participation, and (2) is willing to participate in an HVTN study. Informed consent encompasses all written or verbal study information HVTN CRS staff provide to the participant, before and during the trial. HVTN CRS staff will obtain informed consent of participants according to HVTN policies and procedures.

The informed consent process continues throughout the study. Key study concepts should be reviewed periodically with the participant and the review should be documented. At each study visit, HVTN CRS staff should consider reviewing the procedures and requirements for that visit and for the remaining visits.

Additionally, if any new information is learned that might affect the participants' decisions to stay in the trial, this information will be shared with trial participants. If necessary, participants will be asked to sign revised ICFs.

An HVTN CRS may employ recruitment efforts prior to the participant consenting. For example, some HVTN CRSs use a telephone script to prescreen people before they come to the clinic for a full screening visit. Participants must sign a screening or protocol-specific consent before any procedures are performed to determine eligibility. HVTN CRSs must submit recruitment and prescreening materials to their IRB/EC and any applicable RE for human subjects protection review and approval.

Note: As defined in the DAIDS Protocol Registration Manual, an RE is "Any group other than the local IRB/EC responsible for reviewing and/or approving a clinical research protocol and site-specific ICFs prior to implementation at a site." CRSs are responsible for knowing the requirements of their applicable REs.

#### 9.1.1 Screening consent form

Without a general screening consent, screening for a specific study cannot take place until the site receives protocol registration from the DAIDS RSC Protocol Registration Office.

Some HVTN CRSs have approval from their IRB/EC and any applicable RE to use a general screening consent form that allows screening for an unspecified HIV vaccine trial. In this way, HVTN CRS staff can continually screen potential participants and, when needed, proceed quickly to obtain protocol-specific

enrollment consent. Sites conducting general screening or prescreening approved by their IRB/EC and any applicable RE may use the results from this screening to determine eligibility for this protocol, provided the tests are conducted within the time periods specified in the eligibility criteria.

### **9.1.2 Protocol-specific consent forms**

The protocol-specific consent forms describe the study products to be used and all aspects of protocol participation, including screening and enrollment procedures. A sample protocol-specific consent form for the study is located in [Appendix A](#). A separate sample consent form for other uses of specimens is located in [Appendix C](#).

Each HVTN CRS is responsible for developing a protocol-specific consent form(s) for local use, based on the sample protocol-specific consent forms in [Appendix A](#) and [Appendix C](#). The consent form(s) must be developed in accordance with requirements of the following:

- CRS's IRB/EC and any applicable REs,
- CRS's institution, and
- Elements of informed consent as described in Title 45, CFR Part 46 and Title 21 CFR, Part 50, and in the International Conference on Harmonisation (ICH) E6, GCP: Consolidated Guidance 4.8.

Study sites are strongly encouraged to have their local CABs review their sites-specific consent forms. This review should include, but should not be limited to, issues of cultural competence, local language considerations, and the level of understandability.

The sample informed consent forms include instructions throughout the document for developing specific content.

Regarding protocol registration, sites should follow procedures outlined in the current version of the DAIDS Protocol Registration Manual.

### **9.1.3 Assessment of Understanding**

Study staff are responsible for ensuring that participants fully understand the study before enrolling them. This process involves reviewing the ICF with the participant, allowing time for the participant to reflect on the procedures and issues presented, and answering all questions completely.

An Assessment of Understanding is used to document the participant's understanding of key concepts in this HIV vaccine trial. The participant must complete the Assessment of Understanding before enrollment. Staff may provide assistance in reading and understanding the questions and responses, if necessary.

Participants must verbalize understanding of all questions answered incorrectly. This process and the participant's understanding of the key concepts should be recorded in source documentation at the site.

IRB/EC and any applicable RE may require that a participant has signed either a screening or protocol-specific consent document prior to administering the Assessment of Understanding. The consent process (including the use of the Assessment of Understanding) should be explained thoroughly to the IRB/EC and any applicable RE, whose recommendations should be followed.

## 9.2 Pre-enrollment procedures

Screening may occur over the course of several contacts/visits, up to and including before vaccination on day 0. All inclusion and exclusion criteria must be assessed within 28 days before enrollment, unless otherwise specified in the eligibility criteria (or below in this section).

After the appropriate informed consent has been obtained and before enrollment, the following procedures are performed:

- Medical history, documented in the case history record, to include medical records review for verification of the diagnosis of SLE where appropriate, and for the presence of any exclusionary medications/conditions;
- Assessment of whether the volunteer is at low risk for HIV infection
- Complete physical examination, including height, weight, vital signs, and clinical assessments of head, ears, eyes, nose, and throat; neck; lymph nodes; heart; chest; abdomen; extremities; neurological function; and skin
- Assessment of concomitant medications the volunteer is taking, including prescription and nonprescription drugs, vitamins, topical products, alternative/complementary medicines (eg, herbal and health food supplements), recreational drugs, vaccinations, and allergy shots
- SLE assessment, as determined by a rheumatologist or designee, using standard instruments for this purpose (SELENA-SLEDAI, including Complement profile [C3/C4/CH50] and anti-dsDNA, and SLICC/ACR); and functional status assessment by a staff member using RAPID3;
- Laboratory tests as defined in the inclusion and exclusion criteria, including:
  - Screening HIV test
  - HBsAg
  - Anti-HCV antibodies
  - Syphilis test

- CBC with differential and platelets
  - Chemistry panel (ALT, AST, and creatinine)
  - Complement Profile (C3/C4/CH50)
  - HbA1C
  - Anti-DNA, Double Stranded (Anti-dsDNA)
  - Urinalysis (as described in section 9.7)
  - Urine or serum pregnancy test (participants who were born female), in accordance with local regulatory requirements
- Administration of behavioral risk assessment questionnaire
  - Obtaining of volunteer demographics in compliance with the NIH Policy on Reporting Race and Ethnicity Data: Subjects in Clinical Research, Aug. 8, 2001 (available at <http://grants.nih.gov/grants/guide/notice-files/NOT-OD-01-053.html>)
  - Counseling on HIV testing and risk reduction, performed in compliance with the US Centers for Disease Control and Prevention (CDC)'s current guidelines or other local guidelines for HIV counseling, testing, and referral as described in Section 9.5
  - Discussion of pregnancy prevention. A pregnant or breastfeeding person may not be enrolled in this trial. Specific criteria and assessment of contraception and pregnancy status are described in study inclusion criteria. Discussion of pregnancy prevention includes advising a participant who was assigned female sex at birth and who reports no current sexual activity that could lead to that participant becoming pregnant to have a plan to begin adequate birth control. This plan would be put to use if, during the study, the participant becomes sexually active in a way that could lead to that participant becoming pregnant.

### 9.3 Enrollment and vaccination visits

Enrollment is simultaneous with first vaccination.

At all vaccination visits, the following procedures are performed before vaccination:

- Complete physical examination, including weight, vital signs, and clinical assessments of head, ears, eyes, nose, and throat; neck; lymph nodes; heart; chest; abdomen; extremities; neurological function; and skin;
- CBC/differential/platelets;

- SLE assessment, as determined by a rheumatologist or designee, using standard instruments for this purpose (SELENA-SLEDAI, including Complement profile [C3/C4/CH50] and anti-dsDNA); and functional status assessment by a staff member using RAPID3. Lab results for assessing SLE status must be conducted within 28 days of vaccination and can include using results from a prior visit;
- Assessment of baseline reactogenicity parameters;
- Assessment of concomitant medications (as described in Section 9.2);
- Assessment of any new or unresolved AEs/intercurrent illnesses;
- Serum or urine pregnancy test, in accordance with local regulatory requirements, (for participants who were assigned female sex at birth). Persons who are NOT of reproductive potential due to having undergone total hysterectomy or bilateral oophorectomy (verified by medical records) are not required to undergo pregnancy testing;
- Urinalysis (see Section 9.7); and
- Specimen collection (should be completed prior to vaccination)

Following completion of all procedures in the preceding list, and if results indicate that vaccination may proceed, vaccination is prepared and administered (see Sections 8.3 and 8.4).

Immediately following vaccination, the participant remains in the clinic for observation. An initial reactogenicity assessment is made at a target of 30 minutes after injection, with an acceptable range of 25-60 minutes. Before leaving the clinic, the participant is given the Participant Diary and is instructed on how to complete it. The site will make arrangements to be in contact with the participant during the reactogenicity period (as described in Section 9.8).

The following procedures will be performed at all vaccination visits. These procedures may be performed prior to or following vaccination:

- Risk reduction counseling (as described in Section 9.5);
- Pregnancy prevention assessment (as described in Section 9.2 and 9.6); and
- Assessment of new or unresolved social impacts (site staff will ask participant about the status of any unresolved social impacts and if s/he has experienced any new social impacts as a result of the trial participation).

Additional procedures will be performed at scheduled visits as specified in Appendix F.

- Behavioral risk assessment; and
- Confirm that participants received HIV test results from previous visit. If not, provide test results and post-test counseling as appropriate.

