## Appendix E Laboratory procedures

Procedure	Ship to 	Assay Location 	Tube 	Tube size (vol. capacity) 	Tube volume (mL)														Total	
					1	2	3	4	5	6	7	8	9	10	11	12 	13	14		
					Screening	D0	D7	D14	D28	D35	D42	D84	D168	D175	D182	D210	D238	D364		
Month:	visit 	M0	M0.25	M0.5	M1	M1.25	M1.5	M3	M6	M6.25	M6.5	M7.5	M8.5	M12						
					AIDSVAX B/E				AIDSVAX B/E				AIDSVAX B/E							
BLOOD COLLECTION																				
Screening or diagnostic assays																				
Screening HIV test	Local Lab	Local Lab	SST	5mL	5	—	—	—	—	—	—	—	—	—	—	—	—	—	5	
HBsAg/anti-HCV	Local Lab	Local Lab	SST	5mL	5	—	—	—	—	—	—	—	—	—	—	—	—	—	5	
Syphilis	Local Lab	Local Lab	SST	5mL	5	—	—	—	—	—	—	—	—	—	—	—	—	—	5	
HIV diagnostics 	UW-VSL	UW-VSL	EDTA	10mL	—	—	—	—	—	—	10	—	—	10	—	—	—	20 	40	
Safety labs																				
Hb A1C	Local lab	Local lab	EDTA	5mL	5	—	—	—	—	—	—	—	—	—	—	—	—	—	5	
CBC/ Diff/ platelets	Local lab	Local lab	EDTA	5mL	5	5	5	5	5	5	5	5	5	5	5	5	5	5	60	
Chemistry panel 	Local lab	Local lab	SST	5mL	5	—	—	5	—	—	5	5	—	—	5	—	5	—	30	
Complement profile C3/C4/CH50	Local lab	Local lab	SST	5mL	5	5	5	5	5	5	5	5	5	5	5	5	5	5	60	
Anti-dsDNA	Local lab	Local lab	SST	5mL	5	5	5	5	5	5	5	5	5	5	5	5	5	5	60	
Immunogenicity assays																				
Host genetics 	CSR	HVTN Labs	ACD	8.5mL	—	17	—	—	—	—	—	—	—	—	—	—	—	—	17	
Cellular assays																				
ICS	CSR	HVTN Labs	ACD	8.5mL	—	25.5	—	—	—	—	—	—	—	—	25.5	—	—	—	25.5	76.5
T and B cell phenotyping	CSR	HVTN Labs	ACD	8.5mL	—	34	—	—	—	42.5	17	—	42.5	42.5	34	—	—	34	246.5	
Memory B cell sorts and recombinant Ab production	CSR	Non-HVTN Labs at Duke-DHVI	ACD	8.5mL	—	—	—	—	—	—	25.5	—	—	—	25.5	—	—	51	102	
Plasma cell sorts for B cell repertoire analysis	CSR	Non-HVTN Labs at Duke-DHVI	ACD	8.5mL	—	—	—	—	—	—	—	—	—	—	25.5	—	—	—	25.5	
Humoral assays																				
Binding Ab	CSR	HVTN Labs	SST	8.5mL	—	8.5	—	—	—	—	8.5	—	8.5	—	8.5	—	—	8.5	42.5	
Neutralizing Ab	CSR	HVTN Labs	SST	8.5mL	—	8.5	—	—	—	—	8.5	—	8.5	—	8.5	—	—	8.5	42.5	
ADCC	CSR	HVTN Labs	SST	8.5mL	—	y	—	—	—	—	y	—	y	—	y	—	—	y	0	
bnAb epitope binding and blocking assays	CSR	Non-HVTN Labs at Duke-DHVI	ACD	8.5mL	—	z	—	—	—	—	z	z	—	z	z	z	—	—	z	0
Innate immunity																				
Serum cytokines	CSR	HVTN Labs	SST	5mL	—	5	—	—	—	5	5	—	5	5	5	—	—	5	35	
Sequencing																				

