## Appendix F Procedures at HVTN CRS

Visit:	01 	02	03	04	05	06	07	08	09	10	11	12	13	14
Day:		D0	D7	D14	D28	D35	D42	D84	D168	D175	D182	D210	D238	D364
Month:		M0	M0.25	M0.5	M1	M1.25	M1.5	M3	M6	M6.25	M6.5	M7.5	M8.5	M12
Procedure	Scr.	VAC1			VAC2				VAC3					
Study procedures														
Signed screening consent (if used)	X	—	—	—	—	—	—	—	—	—	—	—	—	—
Assessment of understanding	X	—	—	—	—	—	—	—	—	—	—	—	—	—
Signed protocol consent	X	—	—	—	—	—	—	—	—	—	—	—	—	—
Medical history	X	—	—	—	—	—	—	—	—	—	—	—	—	—
Complete physical exam	X	X	X	X	X	X	X	X	X	X	X	—	X	X
Risk reduction counseling 	X	X	X	X	X	X	X	X	X	X	X	—	X	X
Pregnancy prevention assessment 	X	X	X	X	X	X	X	X	X	X	X	—	X	X
Behavioral risk assessment 	X	—	—	—	—	—	—	X	X	—	—	—	X	X
Confirm eligibility, obtain demographics	X	—	—	—	—	—	—	—	—	—	—	—	—	—
Social impact assessment	—	X	X	X	X	X	X	X	X	X	X	—	X	X
Social impact assessment questionnaire	—	—	—	—	—	—	—	X	X	—	—	—	—	X
Concomitant medications	X	X	X	X	X	X	X	X	X	X	X	—	X	X
Intercurrent illness/adverse experience	—	X	X	X	X	X	X	X	X	X	X	—	X	X
HIV infection assessment 	X	—	—	—	—	—	X	—	—	—	X	—	—	X
Confirm HIV test results provided to participant	—	X	—	—	—	—	—	X	—	—	—	—	X	—
SLE status assessment/functional assessment 	X	X	X	X	X	X	X	X	X	X	X	—	X	—
Health assessment contact 	—	—	—	—	—	—	—	—	—	—	—	X	—	—
Local lab assessment														
Urinalysis and spot urine protein;creatinine ratio	X	X	X	X	X	X	X	X	X	X	X	—	X	—

HVTN 121 Version 2.0 / September 14, 2018

Visit:	01 	02	03	04	05	06	07	08	09	10	11	12	13	14
Day:		D0	D7	D14	D28	D35	D42	D84	D168	D175	D182	D210	D238	D364
Month:		M0	M0.25	M0.5	M1	M1.25	M1.5	M3	M6	M6.25	M6.5	M7.5	M8.5	M12
Procedure	Scr.	VAC1			VAC2				VAC3					
Pregnancy (urine or serum HCG) 	X	X	—	—	X	—	—	—	X	—	—	—	—	—
CBC, differential/platelets	X	X	X	X	X	X	X	X	X	X	X	—	X	—
Chemistry panel (see Section 9.2)	X	—	—	X	—	—	X	X	—	—	X	—	X	—
Syphilis, Hepatitis B, Hepatitis C	X	—	—	—	—	—	—	—	—	—	—	—	—	—
Complement profile (C3/C4/CH50)	X	X	X	X	X	X	X	X	X	X	X	—	X	—
Anti-dsDNA	X	X	X	X	X	X	X	X	X	X	X	—	X	—
Vaccination procedures														
Vaccination 	—	X	—	—	X	—	—	—	X	—	—	—	—	—
Reactogenicity assessments 	—	X	—	—	X	—	—	—	X	—	—	—	—	—

 Enrollment and screening visits can occur on the same day

 For specimen collection requirements, see [Appendix E](#).

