 Includes transmission risk reduction counseling for HIV-infected participants.

 Pregnancy prevention assessment is required only for participants who were assigned female sex at birth and are capable of becoming pregnant.

 Not applicable to HIV-infected participants.

 Includes pre-test counseling and HIV testing. A subsequent follow-up contact is conducted to provide post-test counseling and to report results to participant. If a participant has a confirmed diagnosis of HIV infection, do not perform HIV infection assessment.

 SELENA-SLEDAI, RAPID3. SLICC/ACR at screening only.

 CRS staff and study participants will be in contact to collect information about their health (see HVTN 121 SSP).

 For participants with a confirmed diagnosis of HIV infection, only specimens listed under “Safety labs,” urinalysis, spot urine protein:creatinine ratio, and pregnancy tests specified in [Appendix E](#) will be collected.

 For a participant who was assigned female sex at birth, pregnancy test must be performed on the day of vaccination prior to vaccination. Pregnancy test to determine initial eligibility may be performed at screening, but must also be done on day 0 prior to first vaccination. Persons who are NOT of reproductive potential due to having undergone total hysterectomy or bilateral oophorectomy (verified by medical records), are not required to undergo pregnancy testing. Serum pregnancy tests may be used to confirm the results of, or substitute for, a urine pregnancy test, in accordance with local regulatory requirements.

[figure not shown]
 Not applicable to HIV-infected participants.

 Blood draws required at vaccination visits must be performed prior to administration of study product; however, it is not necessary to have results prior to administration, except for results of a serum pregnancy test, if indicated. Lab tests may be drawn within the 3 days prior to vaccination.

 Reactogenicity assessments performed daily for at least 7 days postvaccination (see Section 9.8)

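### Appendix F footnote 12 conflicts with Section 9.3 on whether SLE blood results must be in hand before vaccination, and the visit schedule does not resolve the conflict at dose 3

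*Combined protocol and SAP*

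**What the plan says.** Section 9.3 lists what is done before the injection at every vaccination visit. The list includes a CBC and an SLE assessment by a rheumatologist or designee using SELENA-SLEDAI, with complement and anti-dsDNA named as part of it. On the age of the labs it states: "Lab results for assessing SLE status must be conducted within 28 days of vaccination". Results from a previous visit may be used. The dose comes after the whole list: "if results indicate that vaccination may proceed, vaccination is prepared and administered".

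Appendix F footnote 12, attached to the vaccination row, requires blood at vaccination visits to be drawn before the product is given, but adds that "it is not necessary to have results prior to administration, except for results of a serum pregnancy test, if indicated". It also allows an early draw: "Lab tests may be drawn within the 3 days prior to vaccination".

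The Appendix E row "Complement profile C3/C4/CH50", its neighbours for anti-dsDNA and CBC, and the Appendix F row "SLE status assessment/functional assessment" all show assessments on Day 84 and Day 168 and nothing between.

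**The concern.** One instruction makes the dose depend on results; the other says that results need not be available. Where recent results are already on file this does little harm. Where they are not, a site can follow the footnote and miss the requirement in Section 9.3.

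What is at stake is information for the person deciding whether to proceed. The required pre-dose SELENA-SLEDAI cannot be completed while complement and anti-dsDNA are pending. Section 7.3.3 makes a rheumatologist's clinical judgement of a flare a reason to stop vaccination, and that judgement would lack these values. Dose 3 is the last dose, so labs on Days 175 and 182 cannot inform any vaccination decision. The note to Table 4-1 says that the risk of this vaccine worsening autoimmune disease is unknown.

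**Working it through.** **Inputs.** Dose days 0, 28 and 168 (Table 3-1). CBC, complement and anti-dsDNA at screening and on Days 0, 7, 14, 28, 35, 42, 84, 168, 175, 182 and 238 (Appendix F). As a check on this reading of the table, 12 draws × 5 mL = 60 mL per test, which matches the Appendix E row totals. Age limit 28 days (Section 9.3). Pre-draw allowance 3 days (footnote 12). The 28 days is a rule and not a derived figure, so there is nothing to reproduce.

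**Age of the last earlier scheduled result = dose day − last earlier draw day.**

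| Dose | Last earlier scheduled draw | Age | Within 28 days? |
|---|---|---|---|
| 1 (Day 0) | Screening | at most 28 days (Sections 7 and 9.2) | Yes |
| 2 (Day 28) | Day 14 | 28 − 14 = 14 days | Yes |
| 3 (Day 168) | Day 84 | 168 − 84 = 84 days | No; 84 − 28 = 56 days over |

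For dose 3 a qualifying result must come from Day 168 − 28 = Day 140 or later. The only scheduled draw in that range is the dose-3 draw, taken between Day 165 (168 − 3) and Day 168. That is the draw whose results footnote 12 says need not be back.

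**What would be missing from the score.** The Appendix G weights give 8 × 8 + 6 × 4 + 7 × 2 + 3 × 1 = 64 + 24 + 14 + 3 = 105 points over 24 items. Low complement (2) and raised DNA binding (2) make 4 points over 2 items. If the CBC is also pending, low platelets (1) and low leukocytes (1) bring this to 6 points over 4 items.

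**What those points could trigger.** New low complement plus raised anti-dsDNA adds 4 points. That satisfies the Appendix G criterion of a rise of at least 3 points and the working flare definition in Section 6.1.1.2, a rise of 4 or more. Set against the dosing rules:

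- Section 7.3.1 lists blood products, other vaccines, allergy injections and "abnormal vital signs or clinical symptoms that may mask assessment of vaccine reaction". It does not name complement or anti-dsDNA.
- Section 7.3.3 lists no stopping rule that these two results meet on their own.
- The mild and moderate flare definitions in Table 11-8 also need a rheumatologist's determination about prednisone treatment.
- The written stopping rules that react to a blood value itself are a grade 3 or grade 4 lab abnormality judged related. For WBC, Table 11-5 puts grade 3 at 1,000 to 1,499 and grade 4 below 1,000.

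**The case against.** The strongest reply is that the two texts can be read together. Section 9.3 is specific and mandatory. Footnote 12 is a general note about blood drawn at the vaccination visit and does not waive the 28-day limit. On that reading, same-day results may be pending only when qualifying results are already on file. This is the sensible reading, but the protocol does not state it and the footnote carries no cross-reference. At dose 3, moreover, the schedule supplies no earlier qualifying result, so the combined reading forbids what the footnote appears to allow. A softer reading, that only the draw must fall within 28 days, fits poorly with a sentence about lab results and a condition on what the results indicate.

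Four further points stand as limits:

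- **CBC.** It is a separate bullet in Section 9.3, and the 28-day sentence sits in the SLE-assessment bullet. CBC comes under that sentence only in so far as platelets and leukocytes are SELENA-SLEDAI items.
- **Other safeguards.** The physical examination, clinical SLE assessment, RAPID3, urinalysis, and medication and adverse event reviews all precede the dose. The PSRT reviews safety weekly during the injection phase (Section 11.4.2).
- **Compliance is possible now.** These are local-lab tests that may be drawn 3 days early. A site can meet both texts if results return in time; turnaround is not given.
- **Unseen documents.** Visit windows are in the Study Specific Procedures, which may also settle the conflict.

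A reader might infer that the protocol permits dose 3 on 84-day-old results. That holds only for footnote 12 read alone, against an explicit requirement in Section 9.3. A reader might also infer that a pending complement or anti-dsDNA result would have stopped the dose. The documents do not support that either: no listed delay or stopping rule is met by those two results alone, and the score above 4 that marks active lupus is an entry criterion, not a dosing rule.

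**Conclusion.** The conflict is real and confined to blood results. In practice it bites at dose 3 only. There the last earlier scheduled results are nominally 84 days old against a 28-day limit, and footnote 12 removes the need to wait for the one scheduled draw that would qualify. A site relying on the footnote alone could vaccinate with two SELENA-SLEDAI items (4 points) unscored, or four items (6 of 105 points) if the CBC is pending too. The wording applies to everyone who reaches dose 3, at most 16 people. How many would have an abnormal pending result cannot be estimated from the documents.

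This rests on nominal visit days, on no unscheduled labs having been drawn after Day 140, and on the Study Specific Procedures not already resolving it. The loss is input to clinical judgement rather than failure of a listed dosing rule. It should be corrected because one dosing instruction can defeat another that protects participants, and the correction is small. Confidence is medium, mainly because of the unseen procedures.

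**What to change.** Make footnote 12 expressly subject to Section 9.3. Vaccination-visit blood results may be pending only if complement, anti-dsDNA and the CBC values used in SELENA-SLEDAI, from a draw within the preceding 28 days, have been reviewed. At dose 3, draw these tubes up to 3 days ahead, as the footnote already allows, and vaccinate within the visit window once the results have been reviewed.

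No earlier or additional draw is needed. A draw well before Day 165 would give up the pre-dose values close to Day 168 that later safety labs are compared with, and would change the visit schedule. An extra draw of the three 5 mL tubes would raise the 56-day total at Day 182 from 483 to 483 + 15 = 498 mL, so one 5 mL repeat would make 503 mL, over the 500 mL limit in Section 10.2. Taking the same tubes up to 3 days sooner leaves the total at 483 mL.

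The cost is one footnote and, at dose 3, a possible separate blood-draw visit or a short wait. The wait has a limit, since Section 7.3.2 says: "If a participant misses a vaccination and the visit window period for the vaccination has passed, that vaccination cannot be given". The fix therefore assumes that local results return within the pre-draw allowance or, failing that, within the visit window; neither the turnaround nor the window is given in these documents. Drawing ahead of the visit keeps the risk of losing dose 3 low.
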